### **Background and Rationale**

Regular physical exercise is known to influence immune function through modulation of inflammatory and hematological parameters. However, the comparative effects of Whole-Body High-Intensity Interval Training (WB-HIIT) and Moderate-Intensity Continuous Training (MICT) on immune markers remain unclear.

### **Objective**

To compare the effects of WB-HIIT and MICT on immune function, inflammatory cytokines, hormonal response, and aerobic capacity in healthy young males.

### **Study Design**

Randomized controlled parallel-group trial.

Group 1: WB-HIIT (Experimental)

Group 2: MICT (Active Comparator)

Duration: 8 weeks

### **Participants**

Healthy male adults aged 18–25 years.

Sample size:  $n = 20$  (10 per group)

### **Intervention**

**WB-HIIT Group:** Whole-body high-intensity interval training performed under supervision, 3–4 sessions/week.

**MICT Group:** Moderate-intensity continuous aerobic training performed under supervision, 3–4 sessions/week.

### **Outcomes**

**Primary Outcomes:** Peripheral immune cell counts (leukocytes, lymphocytes, neutrophils, monocytes) Inflammatory cytokines (IL-6, TNF- $\alpha$ , CRP)

**Secondary Outcomes:** Immunoglobulins (IgA, IgG, IgM) Cortisol levels  $VO_{2max}$

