### **Data Collection**

**Measurements at:** Baseline Post-intervention (8 weeks)

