### **Statistical Analysis**

Normality will be assessed using the Shapiro-Wilk test.

Intergroup comparisons will be made using the independent t-test or the Mann-Whitney U test.

Within-group variations will be analyzed using the paired t-test or the Wilcoxon test. The significance level is set at  $p < 0.05$ .

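### Seven unranked primary outcomes share an undivided two-sided 0.05; if any one significant result counts, the false-positive risk is roughly 11–30%, not 5%

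*Protocol*

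**What the plan says.** In the Protocol, Outcomes, the plural heading "Primary Outcomes" covers four cell counts and three inflammatory markers: "Peripheral immune cell counts (leukocytes, lymphocytes, neutrophils, monocytes) Inflammatory cytokines", the last group being IL-6, TNF-alpha and CRP. That makes seven variables, with no lead outcome and no order.

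The Protocol, Statistical Analysis, then says: "Intergroup comparisons will be made using the independent t-test or the Mann-Whitney U test". It adds: "Within-group variations will be analyzed using the paired t-test or the Wilcoxon test". The closing sentence, beginning "The significance level is set at", fixes 0.05. Item 6 of the Statistical Analysis Plan repeats that level and makes it two-tailed. Data Collection gives two time points, "Baseline Post-intervention (8 weeks"), so each outcome has a single post-baseline value.

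The document's own Statistical Analysis Plan has seven items: data handling, normality, between-group tests, within-group tests, effect size, significance level and software. None contains a multiplicity adjustment, a testing order or a success rule.

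**The concern.** A 5% level describes one test. Here it is attached to seven primary comparisons, and nothing says how the seven results combine into a conclusion. The objective is to compare the two training modes on immune function among other things, and any of the seven markers could be offered as evidence on that. One nominally significant marker out of seven could therefore be reported as a primary effect without departing from the plan, and the stated 5% would not describe the error rate of that conclusion.

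Two features of this trial make it worse. Total leukocytes includes lymphocytes, neutrophils and monocytes, so one chance shift in a subset can appear as two apparently separate primary findings. And with 10 participants per group, real differences of moderate size are hard to detect, so a lone nominal result deserves little trust.

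**Working it through.** **Inputs from the documents**
- Primary outcomes: 4 cell counts + 3 inflammatory markers = 7 (Protocol, Outcomes).
- Level per test: 0.05, two-sided (Protocol, Statistical Analysis; Statistical Analysis Plan, item 6).
- Group size: 10 + 10 (Protocol, Participants), so the t-test has 18 degrees of freedom.
- One post-baseline time point (Protocol, Data Collection).

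**Inputs assumed.** The documents give no correlations between outcomes. Common correlations from 0 to 0.9 are used to show the range. The decision rule is also assumed: at least one significant between-group primary counts as a finding.

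**Step 1: the plan's own figure.** 0.05 is the only error rate stated. It is correct for one test: 1 − 0.95^1 = 0.05. No family-wise rate is given to reproduce.

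**Step 2: seven tests, independent.** 1 − 0.95^7 = 1 − 0.698 = 0.302, about 30%.

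**Step 3: seven tests, correlated.** Null trials were simulated with 10 per group, normal outcomes and seven two-sided t-tests, counting trials with at least one p < 0.05 (and, in the last column, at least one p < 0.05/7).

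| Common correlation | At least one false result at 0.05 | At 0.05/7 |
|---|---|---|
| 0 | 30% | 4.9% |
| 0.3 | 27–28% | 4.7% |
| 0.5 | 23–24% | 4.1% |
| 0.7 | 18–19% | 3.5% |
| 0.9 | 11–12% | 2.0–2.1% |

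The ranges reflect separate simulation runs. At every correlation tried, the 0.05 column is more than twice 5%.

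**Step 4: the overlap among the cell counts.** Building total leukocytes as the sum of its subsets plus a small remainder (assumed SDs: neutrophils 1.3, lymphocytes 0.6, monocytes 0.15, remainder 0.15), with the other correlations set to 0, gives about 28%. The 30% in Step 2 is therefore an upper illustration, not an expected value.

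**Step 5: what the two remedies do to power.** For a true difference of 1 SD with 10 per group, the noncentrality is 1 × √(10/2) = 2.236 on 18 degrees of freedom.
- Single primary at 0.05: critical t = 2.10, power 56%.
- First Holm step at 0.05/7 = 0.0071: critical t = 3.03, power 25%.

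**The case against.** **The decision rule is inferred.** No section says that one significant outcome is enough, and the objective is only to compare effects, with no hypothesis or direction. This stands. The inflation belongs to an any-one-counts reading, and requiring all seven to be significant would remove it. But the plan chooses neither rule, and that silence is itself the defect.

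**The size depends on unknown correlations.** This also stands. A reader might infer 30% as the error rate, or take the upper part of the range as established. The documents do not support that: outcomes that overlap by construction are not independent, and strong correlation brings the figure down to 11–12%.

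**A reader might go further and count every test.** Adding the two within-group tests per outcome gives 21 tests, and adding the five secondary outcomes gives 12 between-group comparisons; treating either set as one independent family yields a much larger figure. The documents do not support either count. The within-group tests use the same participants' data as the between-group test and address a different null hypothesis, namely no change over eight weeks. Rejecting that null is not a claim that one training mode beats the other. The within-group tests are nowhere called primary, and the five further outcomes are expressly secondary.

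**The trial may be exploratory.** With 20 participants and no stated power this is a reasonable reading, but the document does not say so, and it does label seven outcomes as primary.

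**A separate analysis plan might settle it.** That is possible for details left open. Here, however, the document has its own section under that title, with an item on significance level that fixes 0.05 without adjustment.

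**Conclusion.** The concern holds. The plan names seven unranked primary outcomes, attaches an undivided two-sided 0.05 to their comparisons, and gives no rule for what counts as success. If any one significant between-group primary is taken as a finding, the chance of at least one false primary result is roughly 11–30% rather than 5%.

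The figure rests on two assumptions that the documents neither state nor exclude: the any-one-counts rule, and a common correlation between 0 and 0.9. The exact size is uncertain; that it exceeds 5% under this rule is not, since even at a correlation of 0.9 it is more than double. The claim is limited to the seven between-group primary comparisons. It should be settled before the data are analysed.

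**What to change.** Amend the Protocol's Outcomes section and item 6 of the Statistical Analysis Plan in one of two ways.

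- **(a) One primary.** Name one of the seven as the single primary outcome, tested between groups at two-sided 0.05. Report the other six as secondary or exploratory, with estimates and 95% confidence intervals. Cost: no confirmatory claim on those six; no loss of power on the chosen outcome (56% for a 1-SD difference).
- **(b) Keep seven.** Claim a primary effect only where the Holm-adjusted between-group p-value over the seven comparisons is below 0.05. This holds the family-wise error at or below 5% whatever the correlations. Cost: the first step is tested at 0.0071, where power for a 1-SD difference is about 25%.

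Under either option, add a sentence that within-group and secondary results carry no confirmatory claim. Both are wording changes and need no extra participants, visits or assays. With 10 per group, (a) is the more workable choice, provided the outcome is named before any results are seen.

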### **Data Collection**

**Measurements at:** Baseline Post-intervention (8 weeks)

### **Statistical Analysis**

Normality will be assessed using the Shapiro-Wilk test.

Intergroup comparisons will be made using the independent t-test or the Mann-Whitney U test.

Within-group variations will be analyzed using the paired t-test or the Wilcoxon test. The significance level is set at  $p < 0.05$ .

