### **STATISTICAL ANALYSIS PLAN**

#### **1. Data Handling**

Data analyzed using SPSS / R

Missing data handled using listwise deletion

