#### **3. Between-Group Analysis**

Independent samples t-test

Mann–Whitney U test (if non-normal)

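### The only between-group analysis is an unadjusted two-sample test on an unnamed variable; adjusting for the planned baseline would usually gain precision and would remove chance imbalance at almost no cost

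*Protocol*

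**What the plan says.** The design is a "Randomized controlled parallel-group trial" with 10 participants per group (Study Design; Participants). Data Collection gives two measurement times: "Baseline Post-intervention (8 weeks".

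For the comparison of the arms, the Statistical Analysis section states: "Intergroup comparisons will be made using the independent t-test or the Mann-Whitney U test". Section 3 of the statistical analysis plan, Between-Group Analysis, lists the same pair, "Independent samples t-test" and "Mann–Whitney U test (if non-normal".

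The pre/post pair is used explicitly only within each arm: "Within-group variations will be analyzed using the paired t-test or the Wilcoxon test". That analysis does not compare WB-HIIT with MICT.

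No section names a covariate, a change score, or the variable that enters the two-sample test. The file contains its own statistical analysis plan and that plan repeats the unadjusted tests, so the method has been chosen here and not left to a later document.

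**The concern.** The objective is to compare two training programmes, so the between-group test carries the trial's conclusion. Two analyses fit the text, and each has a weakness:

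- **8-week values.** The measured baseline plays no part. A chance baseline difference carries over into the result in proportion to the pre-post correlation.
- **Change scores.** The baseline is subtracted with a fixed coefficient of 1. If the true slope is below 1, this over-corrects, and at low correlation it adds noise.

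ANCOVA estimates the slope from the data and so avoids having to guess between them. With only 10 per arm, lost precision and baseline gaps both matter. Separately, because the analysed variable is not named, either version could be reported for each marker and still be called the planned analysis.

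**Working it through.** **Inputs from the documents.** 10 per group (Participants); two-sided 5% level (Statistical Analysis; section 6 of the analysis plan); baseline and 8-week measurements (Data Collection); unadjusted two-sample tests.

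**Assumptions.** The documents give no effect size, SD, power or pre-post correlation r. I take a true difference of 1 SD, equal SDs at both times, r from 0 to 0.8, and all 20 participants complete. The last is the best case, since the plan says "Missing data handled using listwise deletion" and gives no dropout rate.

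**Plan's own figure.** The sample size of 20 has no stated basis, so there is nothing to reproduce. For orientation, a t-test on 8-week values with 10 per group (18 df) reaches 80% power only for a difference of 1.32 SD.

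**Step 1: variance of the group difference, relative to 8-week values.**

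- 8-week values: 1 (18 df)
- Change scores: 2(1 − r) (18 df)
- ANCOVA: (1 − r²)(1 + 1/(N − 4)) = (1 − r²)(1 + 1/16) = 1.0625(1 − r²) (17 df)

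For example, at r=0.5 ANCOVA gives 1.0625 × 0.75 = 0.797, so the SE ratio is √0.797 = 0.893, a cut of about 11%. The break-even with 8-week values is 1.0625(1 − r²) = 1, so r² = 0.059 and r = 0.24. The lost degree of freedom moves this to about 0.25.

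**Step 2: power for a 1-SD difference (noncentral t).**

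| r | 8-week values | Change scores | ANCOVA | ANCOVA SE vs 8-week values | Difference detectable by ANCOVA, 80% power |
|---|---|---|---|---|---|
| 0 | 56% | 32% | 53% | +3% | 1.37 SD |
| 0.2 | 56% | 39% | 55% | +1% | 1.34 SD |
| 0.3 | 56% | 43% | 57% | −2% | 1.31 SD |
| 0.5 | 56% | 56% | 66% | −11% | 1.19 SD |
| 0.7 | 56% | 78% | 82% | −26% | 0.98 SD |
| 0.8 | 56% | 92% | 93% | −38% | 0.82 SD |

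Simulation (20,000 trials per setting, r from 0.3 to 0.8) agreed with these powers to within about 1 point.

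**Step 3: chance imbalance.** The baseline difference between arms has SD √(2/10) = 0.447 baseline SD. A gap above 0.5 SD has probability 2(1 − Φ(0.5/0.447)) = 2(1 − Φ(1.118)) = 0.264, about 26% per marker.

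Given a baseline gap D, the expected error is rD for 8-week values and (r − 1)D for change scores. At D = 0.5 SD and r=0.7 these are +0.35 SD and −0.15 SD. ANCOVA with the correct slope has none.

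Simulated false-positive rates, only among trials with a gap above 0.5 SD:

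| r | 8-week values | Change scores | ANCOVA |
|---|---|---|---|
| 0.3 | 7% | 11% | 5% |
| 0.5 | 10% | 9% | 6% |
| 0.7 | 14% | 7–8% | 5% |
| 0.8 | 15–16% | 7% | 5–6% |

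Over all randomisations together, every method stays at about 5%.

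**Step 4: skewed markers.** For a simulated log-normal marker (log-SD 1, shift of 1 log-SD, both assumed), two separate runs gave these powers:

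| r | ANCOVA, raw scale | Mann-Whitney, 8-week values | ANCOVA, log scale (one run) |
|---|---|---|---|
| 0.3 | 37–38% | 52% | 58% |
| 0.5 | 41–42% | 51–52% | 66% |
| 0.7 | 54% (one run) | 50% (one run) | 82% |

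For such a marker, untransformed ANCOVA would be worse than the planned rank test at r=0.3 and 0.5. On the log scale it is better throughout.

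**The case against.** The strongest reply is that an unadjusted test in a randomised trial is a legitimate analysis. That stands. Its overall error rate is about 5%, and a reader who infers from the rates in step 3 that the trial inflates its type I error would be wrong: those rates apply only after selecting trials with a sizeable gap.

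Three other strong readings go beyond the documents:

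- **That the plan ignores the baseline.** This is true only if 8-week values are tested, and the text does not say so. On change scores the baseline is used, though with a fixed coefficient.
- **That adjustment always narrows the interval.** It does not below about r=0.25. Against change scores the gain is small at high correlation: 78% to 82% at r=0.7 and 92% to 93% at r=0.8. The documents give no value of r.
- **That an imbalance above 0.5 SD in at least one of the seven primary markers is close to certain.** Independence would give 1 − 0.736⁷ = 88%. But lymphocytes, neutrophils and monocytes are subsets of leukocytes. With an assumed common correlation of 0.3, 0.5 or 0.7 the figure is 85%, 78% or 67%. It also counts gaps in baselines that may not predict the outcome. The per-marker 26% is the sounder number.

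It is also fair to say that the open choice between 8-week values and changes is a gap in specification, which naming the variable would close without ANCOVA. It does not support the efficiency argument.

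What survives is that each unadjusted version does poorly over part of the plausible range of r, while ANCOVA never loses more than about 3 points of power to either over the range shown.

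**Conclusion.** The point holds as a matter of efficiency, conditional imbalance and incomplete specification. It is a should-fix. The planned comparison is valid on average under randomisation, but it names no analysed variable and makes no stated use of a baseline that will be measured anyway.

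For an assumed 1-SD difference with complete data, ANCOVA adds about 10 points of power over 8-week values at r=0.5 and about 26 at r=0.7. Over change scores it adds about 14 points at r=0.3 and about 1 at r=0.8. If r is near zero it costs up to about 3 points against 8-week values. These sizes rest on assumed effect and correlation values and, for normal-theory ANCOVA, on a scale where the marker is roughly normal. The 26% imbalance figure needs only the planned 10 per arm and a normal approximation.

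**What to change.** In the protocol's Statistical Analysis section and in section 3 of the analysis plan, replace the between-group sentence with wording such as:

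*For each outcome, the groups will be compared by ANCOVA of the 8-week value on randomised group and the baseline value of the same outcome. Skewed markers, such as the cytokines and CRP, will be log-transformed at both time points; where a log scale does not suffice, a rank-based ANCOVA will be used. The main result is the adjusted WB-HIIT minus MICT difference, or ratio for log-transformed markers, with its 95% CI.*

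Name the markers to be log-transformed before the outcome data are seen. This wording also fixes the analysed variable, which closes the choice between 8-week values and changes. The within-group tests can stay as description, but should not stand in for the comparison of arms.

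The cost is a few sentences and one residual degree of freedom per model (17 instead of 18). No further participants, visits or measurements are needed.

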#### **4. Within-Group Analysis**

Paired t-test

Wilcoxon signed-rank test

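### Pre-post tests within each arm share the 0.05 level of the between-arm test, and nothing says that only the between-arm test answers the objective

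*Protocol*

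**What the plan says.** The Objective is comparative: "To compare the effects of WB-HIIT and MICT on immune function, inflammatory cytokines, hormonal response, and aerobic capacity". Study Design describes a "Randomized controlled parallel-group trial" in which MICT is the active comparator. Participants gives 10 men per group, and Data Collection gives two measurement times, baseline and 8 weeks.

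The Statistical Analysis section names two families of tests. For the arms against each other: "Intergroup comparisons will be made using the independent t-test or the Mann-Whitney U test". For each arm against its own baseline: "Within-group variations will be analyzed using the paired t-test or the Wilcoxon test". One threshold of 0.05 follows, introduced by "The significance level is set at", with no distinction between the families.

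The Statistical Analysis Plan part of the same document repeats this. Section 3 covers the between-group tests. Section 4, headed "Within-Group Analysis", lists the paired t-test and the "Wilcoxon signed-rank test". Section 6 sets a single two-tailed 0.05. The within-arm tests are nowhere called descriptive, supportive or exploratory, and no sentence says what may be concluded from them.

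**The concern.** A paired test in one arm asks whether that arm moved from its own baseline. It makes no use of the randomised comparison and does not answer the stated objective. If one arm reaches 0.05 and the other does not, the two p-values can lie on either side of the threshold by chance while the true changes are equal. The difference between a significant and a non-significant result has not itself been tested.

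The plan leaves room for that inference because both families have the same level and neither is ranked. With 10 per arm the between-arm test has limited power, so within-arm p-values may be the only significant results available when the trial is reported. What is at stake is a claim that one programme outperforms the other, based on tests that never compared them.

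**Working it through.** The document gives no effect size, standard deviation or power, so there is no planned figure to reproduce. The calculation below illustrates the size of the problem under assumed changes.

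**Inputs from the document.** n = 10 per arm (Participants); two-sided alpha 0.05 (Statistical Analysis Plan, section 6); paired t-test within each arm (section 4); independent t-test between arms (section 3).

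**Assumed.** The standardised change d (mean change divided by the SD of change) is the same in both arms and is varied from 0 to 1.5. Changes are normally distributed, the arms are independent and no data are missing.

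**Step 1: power within one arm.** The paired t statistic has 9 degrees of freedom and noncentrality d × √10. The two-sided critical value is 2.262. Power p is the probability that the absolute value of the statistic exceeds it. At d = 0.5, for example, the noncentrality is 0.5 × 3.162 = 1.581 and p = 0.293.

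**Step 2: chance that exactly one arm is significant.** With equal power in two independent arms this is 2p(1 − p). At d = 0.5 it is 2 × 0.293 × 0.707 = 0.414.

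| d (assumed) | p within one arm | 2p(1 − p) |
|---|---|---|
| 0 | 0.050 | 9.5% |
| 0.3 | 0.136 | 23.5% |
| 0.5 | 0.293 | 41.4% |
| 0.7 | 0.506 | 50.0% |
| 0.8 | 0.616 | 47.3% |
| 1.0 | 0.803 | 31.6% |
| 1.2 | 0.920 | 14.7% |
| 1.5 | 0.987 | 2.5% |

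The true changes are identical in every row, so each figure is the rate at which the one-arm-only reading would declare a difference that does not exist. It applies to a single outcome.

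**Step 3: check by simulation.** In 100,000 simulated trials at each of d = 0.5, 0.7 and 1.0, exactly one arm was significant in 41.3%, 49.9% and 31.4%. In the same trials, an independent t-test of change between the arms was falsely significant in 4.9%, 5.0% and 5.0%.

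**Step 4: power of the between-arm test.** With 18 degrees of freedom and noncentrality d × √(10/2), where d is now a true standardised difference between arms, power is 18.5% at 0.5, 39.5% at 0.8 and 56.2% at 1.0. A non-significant between-arm result is therefore likely at 0.5 and 0.8, and occurs in 43.8% of trials at 1.0.

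**Step 5: number of within-arm tests.** Outcomes lists seven primary measures (four cell counts, three inflammatory markers) and five secondary ones (three immunoglobulins, cortisol, VO2max). Two arms give 2 × 7 = 14 within-arm tests on the primary outcomes and 2 × 12 = 24 on all outcomes.

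**The case against.** The strongest reply is that the harm needs a decision rule that the document does not contain. A direct between-arm test is planned and is listed before the within-arm test in both places. Nowhere does the plan say that an arm difference will be inferred from paired tests. Each paired test keeps its nominal 5% for its own null hypothesis of no change, subject to its usual assumptions. The discordance rates are thus not the error rate of any planned test, and they depend on assumed effects: they fall to 14.7% at 1.2 and 2.5% at 1.5. All of this stands, and it limits the weight of the point.

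A reader might also infer that the lack of an untrained arm is a defect. The documents do not support that. The objective is to compare two programmes, a randomised active comparator serves it, and no passage claims an effect of training as such. Calendar time would matter only if within-arm change were attributed to training. Regression to the mean and assay drift are not supported as specific faults either: Participants sets no threshold on a baseline marker, and nothing is said about how samples are batched.

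What the reply does not remove is that the within-arm tests are written in with the same level and no subordinate status, so nothing in the plan bars the faulty reading.

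**Conclusion.** The point holds at moderate severity. The plan specifies within-arm significance tests that do not address its only objective, and it does not say that conclusions about the two programmes rest on the between-arm comparison.

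If the one-arm-only reading were made, the false-difference rate per outcome would be about 10% to 50% for assumed standardised changes from 0 to 1.2, peaking near 0.7, and below 5% by 1.5. A direct test of change gives about 5%. These rates rest on equal true changes, normality, complete data and 10 per arm.

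It would be too strong to infer that the trial lacks a between-arm analysis, or that the paired tests damage it. The planned between-arm test remains, and its type I error is unaffected by running paired tests beside it.

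**What to change.** In the protocol's Statistical Analysis section and in sections 3 and 4 of the Statistical Analysis Plan:

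- State that any conclusion about WB-HIIT versus MICT rests only on the between-arm comparison of 8-week values adjusted for baseline (ANCOVA), reported with a 95% confidence interval.
- Replace the paired t-test and Wilcoxon test with a descriptive report of within-arm mean change and its 95% confidence interval, without significance claims and without attributing the change to training.

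The cost is small. No participants, visits or assays are added, since the baseline is already measured. The sponsor loses within-arm p-values that do not answer its objective. The between-arm model does change, from an unadjusted two-sample test to one with a baseline covariate, so this is a modest change of method as well as of wording, and it touches protocol text as well as the analysis plan. If the sponsor wishes to keep the paired tests, the minimum is one sentence that labels them supportive and bars conclusions about the arms from them.
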